consumed intact cannabis (e.g., cannabis-containing brownies) on drug test results or behavioral evaluation of performance impairment. The pharmacokinetics and associated pharmacodynamics of cannabis administered via vaporization and oral consumption are currently not well understood and need to be better defined in order to evaluate methods of determining whether or not an individual under the influence of cannabis is impaired.

4. Study Procedures

- a. Study design, including the sequence and timing of study procedures (distinguish research procedures from those that are part of routine care).

Protocol Overview. The proposed study will be conducted at the Johns Hopkins Behavioral Pharmacology Research Unit (BPRU). Participants will complete six outpatient drug administration sessions, each lasting approximately 10 hours and separated by at least 1 week. Participants will receive placebo and two active doses of cannabis via two different routes of administration: orally ingested (0mg, 10mg, 25mg) and inhaled vapor (0mg, 5mg, 20mg). Doses were selected based on prior research at the BPRU; the low active doses are expected to produce discriminative drug effects, but not impair performance, and the high doses are expected to produce both discriminative drug effects and performance impairment. Each dose will be administered to each participant using a within-subjects crossover design. Dosing will be clustered by route of administration (e.g., first three sessions will involve oral administration followed by three sessions of vaporization), and route of administration will not be blinded due to difficulties in estimating the exact time of drug effect onset following oral administration. The order of route of administration will be counterbalanced across participants, and the order of doses within each three-session cluster will be randomized. Research volunteers will be recruited until 20 participants have completed the study.

Participants. We will recruit and consent up to 50 research volunteers in order to obtain 20 study completers. We anticipate that some participants may drop out of the study before completion. Based on recent studies using similar methodology, it is estimated that we will need to enroll 30 participants to achieve 20 study completers.

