Outpatient Discharge. Participants will be discharged after completing final assessments (approximately 8.5 hours post-exposure). In 3 prior studies conducted in our laboratory, this timeline has been adequate for healthy adults to resolve any effects from acute doses of cannabis that are equal to or greater than those used in the present protocol. If a study participant indicates the desire to be discharged from the study early, BPRU medical staff will review the self-reported rating of "drug effect" on the most recent subjective drug effect assessment and conduct a brief interview with the participant prior to discharge. At the end of each session, Study staff will compare vital signs and cognitive performance assessments with baseline data and engage in face-to-face conversation with the participant to ensure that they are fit to leave the unit. Cognitive performance tasks obtained include measures of psychomotor ability, working memory and divided attention. If the participant is able to cognitively engage with staff, vital signs are within normative range (HR < 100bpm, SYS BP < 160mmHg, DIA BP < 90mmHg), and performance is not below 10% of baseline, the participant will be cleared to leave without further evaluation. If any of these parameters are not met, medical staff will assess the participant and a formal field sobriety test will be conducted. If the participant reports a drug effect or exhibits behavior indicative of impairment/intoxication, the participant will be asked to remain at the BPRU until the drug effect subsides and they can pass a field sobriety test. If vital signs are out of range, then medical staff will evaluate and make a determination with regards to whether it is safe for participant to be discharged or remain under observation. Participants will not be allowed to drive home; instructions will be provided at the screening session regarding the need to make alternative transportation arrangements. If a participant fails to arrange a ride, taxi transportation home will be coordinated by study staff and provided free of charge.

Study Measures. A battery of measures will be used to assess participant characteristics and drug effects during the study.

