Performance assessments will be conducted on aspects of cognitive/psychomotor functioning known to be sensitive to the acute effects of smoked marijuana and relevant to functioning in the workplace and/or in operating a motor vehicle or heavy machinery. All participants will be trained on the performance tasks to a stable baseline level during the screening session. Tasks include: 1) Divided Attention Task (DAT): Participants simultaneously perform two different simple tasks based on visual stimuli presented on a computer screen. Primary outcome is the accuracy with which they perform the two tasks; 2) Digit Symbol Substitution Task (DSST): Participants must hand type patterns presented to them on a computer screen for 90 seconds. Primary outcomes are accuracy and total number of patterns completed in the allotted time; and 3) a computerized version of the Paced Auditory Serial Addition Task (PASAT): Participants are provided a string of single digit numbers on the computer and must add the total of the prior to integers presented and respond by selecting the answer using the computer mouse on the screen. The primary outcome is a summed score of the number of correct trials during the task. We will also administer a brief (2-minute) cognitive test battery on an iPad. The DRUID App is currently under development as a potential screening tool for identification of impairment in individuals in workplace or roadside settings. The app utilizes tasks that measure similar performance domains as those used in the task battery described above (divided attention, psychomotor ability, working memory), but is much more abbreviated. This will help us determine the relative sensitivity of the app in detecting impairment relative to the more lengthy assessment battery we have traditionally used in our studies. Performance assessments will be completed at baseline, immediately after drug exposure, and 1, 2, 3, 4, 5, 6, and 8 hours post exposure.

Date: May 18, 2018
Principal Investigator: [name]
Application Number: IRB00122849

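### As worded, the discharge rule's performance limit is 10% of baseline, so a participant with a large measured deficit can be cleared without the formal sobriety test

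*Combined protocol and SAP*

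**What the plan says.** The rule is in section 4a, Outpatient Discharge, and applies about 8.5 hours after exposure. At the end of each session "Study staff will compare vital signs and cognitive performance assessments with baseline data" and talk with the participant. Three conditions must hold together for release: adequate engagement with staff, vital signs in range (heart rate under 100 bpm, systolic under 160 mmHg, diastolic under 90 mmHg), and the score condition. If they hold and "performance is not below 10% of baseline, the participant will be cleared to leave without further evaluation". Otherwise: "If any of these parameters are not met, medical staff will assess the participant and a formal field sobriety test will be conducted".

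A further sentence provides a hold: "If the participant reports a drug effect or exhibits behavior indicative of impairment/intoxication, the participant will be asked to remain at the BPRU" until the effect has gone and a field sobriety test is passed. The same paragraph adds "Participants will not be allowed to drive home".

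The rule mentions psychomotor, working-memory and divided-attention tasks but names no score. The performance-assessment text later in section 4a gives several: accuracy on the Divided Attention Task (DAT); for the Digit Symbol Substitution Task (DSST), "Primary outcomes are accuracy and total number of patterns completed in the allotted time"; and the number correct on the Paced Auditory Serial Addition Task (PASAT). These tasks, the DRUID app and the DRE battery are all scheduled at baseline and at hour 8. No section restates, defines or corrects the 10% limit.

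**The concern.** A limit of this kind is there to send a participant with a material loss of performance to a closer examination. Set at 10% of baseline, it does not do that: someone who has lost half or three quarters of baseline performance still meets it. The phrase looks like a slip for a limit of 10% below baseline, but that intent is inferred. Staff on different shifts could apply floors of 10% or 90% to the same participant, and could choose different scores.

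The other routes to assessment do not use the task score. They rest on engagement, vital signs, reported drug effect and observed behavior. The score limit is therefore the one part of the clearing rule that could catch a deficit that all of these miss. The study itself treats subjective effect and objective performance as separate measures. What is at stake is participant safety at discharge; the sample size, power and analysis are not affected.

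**Working it through.** The plan states the limit without deriving it, so there is no figure to reproduce. The check asks what the limit lets through. Let S be the hour-8 score and B the baseline score, with higher scores better (an assumption that fits accuracy and number correct).

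**1. The two readings.**
- As written: clear if S/B ≥ 0.10. Largest deficit cleared = 1 − 0.10 = 90%.
- Likely intent: clear if S/B ≥ 0.90. Largest deficit cleared = 1 − 0.90 = 10%.

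The documents give no baseline scores. With assumed baselines:

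| B | Floor as written (0.10 × B) | Floor if 90% (0.90 × B) |
|---|---|---|
| 40 | 4 | 36 |
| 60 | 6 | 54 |
| 100 | 10 | 90 |

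**2. Which deficits pass.** Deficits of 5% and 10% pass under both readings. Deficits of 15%, 25%, 50%, 75% and 90% pass only as written. A deficit of 95% fails both. The readings differ for every score from 10% up to, but not including, 90% of baseline.

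**3. What else could stop the release.** Poor engagement or an out-of-range vital sign leads to assessment and the sobriety test. A reported drug effect or impaired behavior leads to the hold. The notification limits in section 6a (heart rate above 120 bpm, pressure above 160/90 or below 90/50 mmHg) concern vital signs only. Once all of these are clear, the score is the only remaining condition. The two readings then give different decisions in one situation: a score between 10% and 90% of baseline with nothing else judged abnormal.

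**4. How often the score limit would act.** This needs the SD of the change in score, which the documents do not give. Assume a normal distribution with SD of 5% or 10% of baseline. For a true drop d and limit c, the chance of a flag is Φ((c − (1 − d))/SD).

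| True drop | SD | Limit 0.90 | Limit 0.10 |
|---|---|---|---|
| 20% | 5% | Φ(2) = 97.7% | Φ(−14), effectively 0 |
| 20% | 10% | Φ(1) = 84.1% | Φ(−7), about 1.3 × 10⁻¹² |
| 50% | 5% | Φ(8), over 99.9% | Φ(−8), about 6 × 10⁻¹⁶ |
| 50% | 10% | Φ(4), over 99.9% | Φ(−4) = 0.003% |

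**5. Unneeded flags at the 90% limit.** With no true drop, the chance for one outcome is Φ(−0.10/SD): Φ(−2) = 2.3% at SD 5% and Φ(−1) = 15.9% at SD 10%. Planned completer sessions number 20 × 6 = 120, so this is 120 × 0.0228 = 2.7 to 120 × 0.159 = 19 sessions. If failing any of four outcomes counted, and they were independent, the chance would be 1 − (1 − 0.0228)⁴ = 8.8% to 1 − (1 − 0.159)⁴ = 49.9%.

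**The case against.** The strongest reply is that the participant has been examined objectively shortly before leaving. Section 4a schedules the DRE battery, including walk-and-turn and one-leg stand, at hour 8 of every session, and the DRUID app at the same time. Section 7d speaks of video of field sobriety assessments, which suggests that the plan regards the DRE battery as that kind of test. Staff who had just seen a poor walk-and-turn could well treat it as impaired behavior and apply the hold. The drug-effect questionnaire also continues past hour 8 until no effect is reported. All of this stands, with one limit: the discharge rule neither uses the hour-8 DRE or DRUID results nor sets a pass mark for them.

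A reader might infer three stronger things that the documents do not support.
- That a large deficit leads to release automatically. It does not; the other conditions and the hold still apply.
- That the score limit is the only objective check at discharge, so that participants leave on conversation and self-report alone. The hour-8 battery and the vital-sign limits contradict this.
- That the 40 high-dose sessions (20 × 2) are the number at risk. The Protocol Overview does say "the high doses are expected to produce both discriminative drug effects and performance impairment", but that does not describe the state at 8.5 hours. The sponsor reports that this timeline was adequate in three prior studies at equal or greater doses.

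The reply that the intent is obvious carries some weight, but it is a reason to correct the sentence.

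**Conclusion.** The limit is wrong as written. It lets measured deficits of up to 90% meet the performance criterion, so that criterion almost never leads to the assessment and formal sobriety test. The consequence is conditional: a participant with a large deficit can be cleared without that test when every other condition is satisfied and no behavior is judged impaired.

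The 90% and 10% deficit limits follow from the wording alone. The flagging rates rest on an assumed SD and on normality. The number of participants with a deficit at discharge cannot be derived from the documents. The practical risk is limited, given the hour-8 battery, the ban on driving, the free taxi and the prior experience. The correction should still be made, because this is a participant-safety threshold and the change is small.

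**What to change.** Replace the phrase with: *performance is not more than 10% below that session's baseline (at least 90% of baseline)*. Name the score or scores to which it applies and, if more than one, say whether any one or all must meet it. Naming the session's own baseline also separates it from the training at screening, where participants are "trained on the performance tasks to a stable baseline level during the screening session".

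The change touches one sentence and any discharge checklist; the baseline and hour-8 scores are already collected. The downside is extra assessments of participants with no true drop. The documents do not allow that number to be derived; under the assumed SD of 5-10% it is about 2-16% of sessions for one outcome. Fatigue and hunger, which section 4e acknowledges as influences on the measured effects, could raise it. Requiring 90% on each of four outcomes is not needed to correct the slip and could, under the same assumptions with independence, send up to about half of such sessions to assessment. The sponsor should weigh that when choosing the scores.

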Screening. During the laboratory screening assessment, a battery of measures will be administered to collect background demographic data (age, gender, self-reported race and ethnicity, height, and weight) and to determine study eligibility (e.g. Medical History Interview, Drug-History Questionnaire, and Timeline Follow-Back (TLFB)). A physical examination will be performed on each subject during the Screening Visit. All major organ systems, including head, eyes, ears, nose, and throat (HEENT); cardiovascular system; lungs; abdomen (liver/spleen); extremities; skin; central nervous system (CNS); musculoskeletal system, and general appearance. A 12-lead EKG will be conducted to ascertain cardiovascular health and biological specimens will be tested for routine clinical chemistry, hematology, serology, serum pregnancy test (females only), and for evidence of recent illicit drug use.

Experimental Sessions. Vital signs (heart rate, systolic blood pressure (SBP), diastolic blood pressure (DBP)) will be measured in the seated position at baseline, immediately after administration, and 1, 2, 3, 4, 5, 6, and 8 hours post exposure.

Blood sampling (6 mL per specimen) will occur 8 times during each experimental session. For vaporization sessions, blood will be collected at baseline, immediately after administration, and 1, 2, 3, 4, 6, and 8 hours post exposure. For oral administration sessions, blood will be collected at baseline, 1, 2, 3,

Date: May 18, 2018

Principal Investigator: [name]

Application Number: IRB00122849

4, 5, 6, and 8 hours post exposure. Participants will have an indwelling intravenous catheter inserted prior to the start of the exposure session. Six milliliters of blood will be collected by catheter at designated times into vacutainer tubes (gray top). Blood will be centrifuged and plasma will be divided into three plastic cryotubes, labeled and stored frozen at -80 °C until shipped frozen on dry ice to a designated laboratory for analysis. 48mL of blood will be obtained per session for a total of 288mL of blood across the 6 outpatient sessions.

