A battery of DRE assessments will include currently practiced assessments that have been found to be most sensitive to effects of cannabis impairment (e.g., walk-and-turn, one-leg stand, lack of convergence, and horizontal gaze nystagmus). Eye movements will be recorded using an eye-tracking camera during the assessment, which will include measures of eye convergence, horizontal gaze nystagmus, and pupil size. Note: this eye-tracking camera will gauge which tracking paths produce characteristic involuntary eye movements that a trained officer could observe without the aid of a recording device. We are not proposing that the camera itself would be used in a roadside testing environment. All DRE assessments will be recorded using a web camera which will be set up by the research staff member running the session. The purpose of these recordings is to assure valid ratings on the DRE assessments and to allow for re-coding performance of study completers if new "clues" about impairment are established during the course of the study. Consent for videotaping will be obtained from all study volunteers and video recordings will not be shared outside the study team without additional written consent of the individual study participant. These assessments will be completed at baseline, immediately after exposure, and 1, 2, 3, 4, 5, 6, and 8-hours post exposure.

The eye-tracking camera (e.g. DAX Evidence Recorder) automatically quantifies and assesses the involuntary eye movements (e.g. gaze nystagmus) that occur when a user is asked to visually follow an object (e.g. a pencil moved back and forth). We will evaluate whether cannabis administration impacts gaze nystagmus, eye convergence, and changes in pupil size when ambient room lighting is brightened/darkened. The eye convergence test involves asking the participant to follow the test administrator's finger (or a pencil) with their eyes as it moves from far to close to the nose (without touching the participant).

- b. Study duration and number of study visits required of research participants.

All participants will complete a visit for screening evaluation. Participants meeting eligibility criteria will be enrolled in the study and complete 6 outpatient drug administration sessions, lasting approximately 10 hours each, and spaced at least one week apart.

- c. Blinding, including justification for blinding or not blinding the trial, if applicable.

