where a participant experiences panic and or paranoid reactions, research staff will engage the person in relaxation exercises and will suspend research procedures until the volunteer has regained comfort. These types of effects are typically of short duration. Acute cannabis exposure is expected to result in a time-limited increase in heart rate and orthostatic hypotension. If heart rate increases above 120bpm, blood pressure increases above 160/90mmHg or drops below 90/50mmHg, a nurse practitioner or physician will be notified and will evaluate the study participant. The NP/MD will determine whether there is a need for urgent care versus continued observation and evaluation. In the case of an extreme adverse reaction, study staff will call 911 and EMTs will take participants across the street to the Johns Hopkins Bayview ER for treatment.

- b. Justification and safety information if FDA approved drugs will be administered for non-FDA approved indications or if doses or routes of administration or participant populations are changed.

Not applicable to this protocol.

- c. Justification and safety information if non-FDA approved drugs without an IND will be administered.

Not applicable to this protocol. An IND has been obtained for the administration of cannabis.

Study Statistics

- a. Primary outcome variable.

The primary outcome variables are the quantitative levels of THC and its metabolites in biological matrices (oral, urine, blood), subjective rating of "Drug Effect" on the DEQ, and performance on DRE and cognitive/psychomotor assessments.

- b. Secondary outcome variables.

Secondary outcome variables include subjective drug effect and mood ratings on additional items of the DEQ and vital signs.

- c. Statistical plan including sample size justification and interim data analysis.

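### The plan expects orthostatic hypotension but schedules only seated blood pressures, and its discharge limits have no lower bound to match its own low-pressure trigger

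*Combined protocol and SAP*

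**What the plan says.** Three parts of the document bear on this.

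**Expected effect and trigger (section 6a, adverse-event paragraph).** "Acute cannabis exposure is expected to result in a time-limited increase in heart rate and orthostatic hypotension". The next sentence reads: "If heart rate increases above 120bpm, blood pressure increases above 160/90mmHg or drops below 90/50mmHg, a nurse practitioner or physician will be notified". The limits are absolute values. Neither a posture nor a change on standing is mentioned.

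**Measurement (section 4a, Study Measures, Experimental Sessions).** Heart rate, systolic and diastolic pressure "will be measured in the seated position at baseline, immediately after administration, and 1, 2, 3, 4, 5, 6, and 8 hours post exposure". The DRE battery, which includes "walk-and-turn, one-leg stand, lack of convergence, and horizontal gaze nystagmus", has the same nominal times. The order of vital signs and DRE tests within a time point is not given. The worn cardiac sensor stores a single-lead ECG and accelerometer data for later upload. It does not record blood pressure.

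**Leaving the unit (section 4a, Outpatient Discharge).** Discharge is "approximately 8.5 hours post-exposure". "Study staff will compare vital signs and cognitive performance assessments with baseline data", and one condition for release is that "vital signs are within normative range (HR < 100bpm, SYS BP < 160mmHg, DIA BP < 90mmHg" holds. No lower blood pressure limit is listed, no posture is stated, and the size of change from baseline that would matter is not defined.

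**The concern.** Orthostatic hypotension is a fall in pressure on standing, so a seated reading does not measure it. The plan names the effect, sets a low-pressure trigger in the next sentence, and then fixes a posture for every scheduled reading that cannot show the effect. A participant whose pressure is normal when seated and falls on standing gives the trigger nothing to act on, unless someone takes an unscheduled reading.

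What is at stake is mainly safety monitoring. Participants do standing balance tests at each of these nominal times, starting immediately after exposure. Section 6a also reports dizziness, dose-dependent and in a minority of participants, from the laboratory's earlier oral and vaporized studies. In addition, vital signs are a secondary outcome under Study Statistics, and the data set as planned cannot describe this expected effect.

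**Working it through.** No sample size, power or event rate enters this point, so there is no figure of the plan's to reproduce. The check is a count of scheduled readings and a side-by-side reading of the passages.

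**Inputs**
- Vital-sign times per session (section 4a): baseline, immediately after, and 1, 2, 3, 4, 5, 6 and 8 h. That is 9 sets, of which 9 − 1 = 8 are post-dose.
- Sessions (section 4a, Protocol Overview): oral 0, 10 and 25 mg and vapor 0, 5 and 20 mg. That is 6 sessions, of which 6 − 2 = 4 are active.
- DRE battery times (section 4a): the same 9 nominal times.

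**Count per completer**

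| Quantity | Formula | Result |
|---|---|---|
| Seated sets, all sessions | 9 × 6 | 54 |
| Seated sets, active sessions | 9 × 4 | 36 |
| Post-dose seated sets, active sessions | 8 × 4 | 32 |
| Post-dose DRE batteries, active sessions | 8 × 4 | 32 |
| Standing or postural sets scheduled | – | 0 |

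The relevant figure is 32. The total of 54 includes baselines and both placebo sessions, where the effect is not expected. With 20 completers, 32 × 20 = 640 post-dose sets follow an active dose.

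**Can another planned measurement stand in?**
- The cardiac sensor has no blood pressure channel, and its data are read only after removal.
- The end-of-session comparison with baseline draws on scheduled vital signs, which are seated at both ends.
- Supervision by medical and nursing staff can pick up symptoms or unsteadiness and may prompt an unscheduled reading. It is not a scheduled measurement of pressure.

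**Discharge limits against the trigger**
- Section 6a: a pressure below 90/50 leads to notification and evaluation.
- Outpatient Discharge: systolic below 160 and diastolic below 90 are acceptable.
- Since 90 < 160 and 50 < 90, any pressure below 90/50 satisfies the listed discharge limits. With the other release conditions met, one passage lets the participant go with no further assessment, while the other calls for a nurse practitioner or physician. This holds in any posture.

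**The case against.** The strongest reply is that section 6a never promises a postural measurement, so sections 4a and 6a do not strictly contradict each other, and other safeguards exist. The trigger states no posture, so it also covers any standing reading that staff choose to take. Staff supervise throughout, and the balance tests are watched and video-recorded. All of that stands. It limits the point to what the schedule measures.

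A reader might infer more, in four ways that the documents do not support.

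- **That the effect is expected after every active dose.** Section 6a makes one general statement about acute exposure and calls the effect time-limited. The dizziness reported earlier occurred in a minority and was dose-dependent.
- **That a postural fall would go undetected.** Symptoms, an unscheduled reading or a low seated value could each bring it to light. Only the absence of a scheduled measurement is established. Because the order within a time point is not stated, the documents also do not show whether vital signs come before the balance tests.
- **That a primary outcome is blurred.** Objectives P1 and S3 concern impairment after cannabis and whether DRE tests detect it. A failed balance test caused by a drug-induced fall in pressure is a cannabis effect, not an artefact. No objective asks for separation by mechanism, and placebo sessions within each route control for non-drug factors.
- **That participants routinely leave with an unmeasured postural fall.** Discharge is about 8.5 h after exposure, and the plan says this interval was adequate in three earlier studies at equal or greater doses. A balance battery is done at 8 h, signs of impairment keep the participant on the unit, and driving home is barred. The posture argument is therefore weak at discharge. What remains there is the missing lower limit. Early departure is less fully described: the sentence on it names a review of the drug-effect rating and that staff "conduct a brief interview with the participant prior to discharge", without mentioning vital signs.

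A practical objection also stands in part. Each time point already carries vital signs, the questionnaire, performance tasks and the DRE battery, with blood and oral fluid at most of them. Extra minutes could disturb the sampling times, so placement matters.

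**Conclusion.** The point holds in a limited form. The plan expects orthostatic hypotension, but all 32 post-dose vital-sign sets per completer in the active sessions are seated, and none can show a fall on standing. The posture to which the trigger applies is unstated. The discharge limits and the trigger give different instructions for a pressure below 90/50 and must be reconciled.

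This is a gap in safety monitoring and in consistency. It has no bearing on sample size, error rates or the validity of the DRE outcomes. The documents give no rate of postural falls, so the number that might pass unmeasured cannot be estimated. The conclusion rests on the ordinary meaning of orthostatic hypotension and on the schedule being followed as written. It is worth acting on because the change is small.

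**What to change.** 1. In section 4a, Experimental Sessions, add a standing heart rate and blood pressure reading after the seated one at each post-dose time, and at baseline for reference. State where it falls relative to the DRE tests. Because dose is blinded, it has to be taken in placebo sessions too, giving 9 × 6 = 54 added readings per completer.
2. In section 6a, state whether the notification trigger refers to seated readings, standing readings or both.
3. Reconcile the Outpatient Discharge limits, which have no lower blood pressure bound, with section 6a, which has one. Any threshold or management rule is for the sponsor and study physician to set.

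The cost is taken to be a few extra minutes per assessment block. That is an assumption, as the documents give no timing. It should need no new staff or equipment beyond the cuff already in use and extra fields on the form. The reading should be placed so that it does not shift the blood and oral fluid collections, above all the collection immediately after inhalation.
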